8.7.2 Stopping Rules

Summaries will be provided using counts and percentages for subjects who meets the stopping rules as described below:

- ALT or AST > 5 x Baseline
- ALT or AST > 2 x Baseline AND concomitant total bilirubin > 2 x Baseline OR Concomitant INR > 0.2 from Baseline
- ALT or AST > Baseline AND Right Upper Quadrant Abdominal Pain, Anorexia, Nausea, Vomiting, Fever, Eosinophilia, and/or Rash

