10.1. Individual Subject Stopping Rules

Study drug will be discontinued in subjects with elevated ALT or AST (see below) and thorough evaluation and follow-up will be performed:

- If ALT or AST increases to $>5 \times$ Baseline
- If ALT or AST increase $>2 \times$ Baseline AND the increase is accompanied by a concomitant total bilirubin increase to $>2 \times$ Baseline OR the INR concomitantly increases by >0.2
- If elevations of ALT/AST are accompanied by signs or symptoms of right upper quadrant abdominal pain, anorexia, nausea, vomiting, fever, eosinophilia, and/or rash

For subjects who meet the discontinuation criteria and have evidence of liver injury, additional PK samples will be obtained at the same visits as safety labs.

Please refer to Section 10.2 for the close monitoring for subjects who meet criteria for drug discontinuation due to elevated ALT/AST.

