9. Height to be assessed at Screening only
10. Full physical exam (PE) at screening and EOS Visit; subsequent PE should be targeted to review new signs and symptoms
11. Vital Signs include heart rate, respiratory rate, blood pressure, and will be measured once in the morning before the morning dose of study drug
12. Safety laboratory tests include chemistry (including liver function tests), hematology, and urinalysis and should be collected predose at all visits; See [Table 15](#) for details. Creatinine clearance will be calculated based on serum creatinine value performed all visits.. HbA1c will be obtained at Screening, Baseline, and Week 12 only
13. Lipids and CV risk markers to be collected are detailed in [Table 15](#)
14. Markers of inflammation include fibrinogen, CRP, IL6, IL1 β , TNF- α , TNF- β , alpha2 macroglobulin and haptoglobin (See [Table 15](#))
15. Samples will be collected from all subjects predose. Additional samples may be collected to further assess safety events.
16. Samples should be collected after a minimum 8 hr fast and before the subject takes the daily dose of study drug. All samples collected Day 1, Weeks 2, 4, 8 and 12 at predose and two samples postdose; with the first sample collected 1 to 3 hours postdose and the second sample collected at least 1 hour later
17. Collect PK/PD samples after a minimum 8 hr fast and before the daily dose of study drug. PK/PD samples on Days 1 and 84 (Week12) collected predose and 2, 6, and 8 hr postdose; Weeks 2, 4 and 8 at predose and two samples postdose with the first sample collected 1 to 3 hours postdose and the second sample collected at least 1 hr later
18. PK predose samples should be collected after a minimum 8 hour fast before the daily dose of study drug. PK samples collected Day 1, Weeks 2, 4, 8 and 12 at predose and two samples postdose; the first sample collected 1 to 3 hours postdose and the second sample at least 1 hour later. For subjects with persistent transaminase or ALP elevations, and have evidence of liver injury and who remain on study drug, [REDACTED].
19. Study drug given in the clinic on days where subject is seen in the clinic

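### SAP 8.7.2 tabulates the third hepatic stopping rule without the time link that Protocol 10.1 requires, so an enzyme rise and an unrelated symptom may be counted together

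*SAP*

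**What the plan says.** Protocol 10.1 opens with a condition that covers all three rules: "Study drug will be discontinued in subjects with elevated ALT or AST (see below) and thorough evaluation and follow-up will be performed". Its third rule is "If elevations of ALT/AST are accompanied by signs or symptoms of right upper quadrant abdominal pain, anorexia, nausea, vomiting, fever, eosinophilia, and/or rash". It does not say how large an elevation must be. In its second rule, ALT or AST must exceed twice Baseline together with a bilirubin criterion, and the INR alternative reads "OR the INR concomitantly increases by >0.2". There are no brackets.

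SAP 8.7.2 introduces its table with "Summaries will be provided using counts and percentages for subjects who meets the stopping rules as described below" and then restates the rules. Its third line is "ALT or AST > Baseline AND Right Upper Quadrant Abdominal Pain, Anorexia, Nausea, Vomiting, Fever, Eosinophilia, and/or Rash". Its second line, after the ALT/AST condition, continues "AND concomitant total bilirubin > 2 x Baseline OR Concomitant INR > 0.2 from Baseline".

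On sampling, the notes to the protocol's Schedule of Assessments state: "Safety laboratory tests include chemistry (including liver function tests), hematology, and urinalysis and should be collected predose at all visits". That gives ALT and AST at five post-baseline visits through Week 12 (Day 3 and Weeks 2, 4, 8 and 12), and again at EOS. The schedule marks INR at Screening and EOS only, and the SAP's copy of the schedule agrees.

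**The concern.** The protocol's third rule describes one clinical picture: raised transaminases with symptoms at the same time. The SAP turns it into two separate facts about a subject, joined by AND. A value above Baseline at Week 2 and an unconnected rash at Week 10 satisfy the SAP line. The line directly above it uses the word *concomitant* twice, so the SAP does state a time link where it means to apply one. A programmer has no stated reason to add one to rule 3.

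Rule 2 has a smaller problem. A line of the form A AND B OR C can be read as (A AND B) OR C or as A AND (B OR C). Under the first reading an INR rise qualifies with no transaminase rise.

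At stake is the credibility of a planned safety summary, in a trial whose primary objectives include safety and tolerability. Chance pairings would be reported as subjects who met a hepatic stopping rule.

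**Working it through.** Neither document states an expected count for this table, so there is no planned figure to reproduce.

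**1. Rule 3, side by side.** The protocol has an elevation (size not defined) accompanied by a listed sign or symptom. The SAP has any value above Baseline and a listed sign or symptom, with no timing word, window or same-visit condition. The threshold is the SAP's own reading of an undefined term and contradicts no stated protocol value. The time link is what has been lost.

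**2. Direction.** A subject with a raised enzyme at the visit that matches the symptom also has a raised enzyme at some visit. The time-linked set is therefore contained in the set as written, and the count as written can never be smaller at the same threshold.

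**3. Illustrative size.** The following assumptions are not in the documents: no drug effect; ALT and AST normal and varying independently from visit to visit around a stable level; ALT–AST correlation *r* at a visit from 0 to 0.8; Baseline taken as the last pre-dose value; five post-baseline visits; symptoms unrelated to the enzymes and matched to one visit.

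- One given visit: P(ALT or AST above Baseline) = 1 − [1/4 + arcsin(*r*)/(2π)]. This gives 0.75, 0.667 and 0.602 for *r* = 0, 0.5 and 0.8.
- Any of five visits, *r* = 0: each enzyme's Baseline is the highest of six exchangeable values with probability 1/6, so the result is 1 − (1/6)² = 0.972. Simulation of 400,000 subjects gives 0.972, 0.937 and 0.902 for *r* = 0, 0.5 and 0.8.

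Expected count in an arm of 50 at *r* = 0.5 is 50 × symptom rate × probability:

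| Assumed symptom rate | As written (0.937) | Linked to one visit (0.667) | Excess |
|---|---|---|---|
| 10% | 4.7 | 3.3 | 1.4 |
| 20% | 9.4 | 6.7 | 2.7 |
| 40% | 18.7 | 13.3 | 5.4 |

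In the placebo arm of 25 the excess is half as large: 0.7, 1.4 and 2.7. If both enzymes fall by 1 or 2 within-subject SD, the laboratory half is met by 72% or 38% at any visit, against 37% or 13% at one visit. Adding EOS as a sixth visit raises 0.937 to 0.950. Averaging two pre-dose values as Baseline, still with five visits, raises it to 0.966.

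**4. Rule 2.** Let A be ALT or AST above twice Baseline, B the bilirubin criterion and C the INR criterion. The two groupings differ in two of the eight combinations: C true and A false, with B either way. In both, (A AND B) OR C counts the subject and A AND (B OR C) does not. The protocol's lead-in on elevated ALT or AST, and the word *concomitant* attached to INR, support the second grouping. Under the first, the scheduled INR values available are at EOS, four weeks after the last dose. If the within-subject SD of INR is 0.05 to 0.10 (assumed), the chance of a rise above 0.2 between two measurements is P(Z > 0.2/(0.05√2)) = 0.2% to P(Z > 0.2/(0.10√2)) = 7.9%.

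**The case against.** The SAP's introduction says that it should be read with the protocol, which supplies the missing link. Pairing a Week 2 value with a Week 10 rash is the least natural reading, and the table shells are in a separate document. The table is descriptive: SAP 8.7 plans no safety tests. It does not feed the primary safety endpoint, which is the frequency of adverse events, serious adverse events and those leading to discontinuation. Discontinuations with reasons are tabulated under SAP 8.2, laboratory data are listed, and subjects under close observation have their own listing. Dosing decisions follow Protocol 10.1, not this table.

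The points about consequence stand and keep this minor. The appeal to the protocol does not: SAP 8.7.2 ties its summary to the rules as it describes them, and a general cross-reference does not override a criterion that the SAP has rewritten.

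A reader might infer more than the documents support:

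- *That the SAP drops the time link throughout.* It does so in rule 3 only.
- *That the SAP makes INR alone sufficient.* The missing brackets come from Protocol 10.1. They leave an ambiguity, and how it will be programmed is not shown. Protocol 10.2 also names INR among possible additional tests during close observation, so unscheduled on-treatment values may exist.
- *That the inflation can be sized from the planning assumptions.* Mean ALT changes of −10 and −40 with SD 40 give a single-visit chance of a rise of 40% and 16%. With an assumed visit correlation of 0.3 to 0.7, the chance at any of five visits is 67–82% and 35–48%, about 1.7 to 3 times as high. But this applies sample-size figures for a Week 12 endpoint to every visit, including Day 3, and a symptom lasting over several visits would narrow the gap.
- *That the contrast between arms is diluted.* On those same figures the ratio falls from 2.5 (40/16) to 1.9 (67/35) or 1.7 (82/48), but the absolute gap widens from 24 points to 32 (67 − 35) or 34 (82 − 48).

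**Conclusion.** The point holds for rule 3. The SAP line omits the concurrence that the protocol requires, and subjects whose enzyme rise and symptom are unrelated may be counted as meeting a stopping rule. The direction is certain: the count can only be inflated relative to a time-linked one. The size is not. The illustrative excess of about 1.4 to 5.4 subjects per arm of 50 rests on assumed symptom rates, no drug effect and matching to one visit, and is towards the upper end for symptoms that persist. For rule 2 the finding is an inherited ambiguity that could let an INR rise alone count, depending on programming. The effect is on the accuracy of a descriptive safety table. Neither the primary safety endpoint nor the management of subjects depends on it.

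**What to change.** Reconcile SAP 8.7.2 with Protocol 10.1, for tabulation only:

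- Count rule 3 only when a listed symptom is recorded as an adverse event that is ongoing at the qualifying ALT/AST sample, or that starts within a pre-stated number of days of it.
- Bracket rule 2 as ALT/AST AND (bilirubin OR INR), in line with the protocol's lead-in, once the sponsor confirms that this is the intended grouping.
- Define concurrency in rule 2 by a pre-stated window. Requiring the same sample date could drop true cases, because Protocol 10.2 gives 48–72 hours as an example of prompt reassessment.

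The cost is two amended SAP lines and a date match between adverse-event and laboratory records, settled before unblinding. No new data and no protocol procedure are needed. The thresholds, the meaning of an elevation in rule 3 and all stopping decisions remain for the sponsor to reconcile.

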8.7.2.1 Close Monitoring for Drug Discontinuation due to Elevated ALT/AST

The following close observation guidelines applies to subjects that repeat assessments show persistent elevations of transaminases, but who do not meet drug discontinuation criteria, and for subjects who discontinue study drug due to ALT/AST elevations.

A listing will be used to track and evaluate subjects that are part of the close observation guidelines. Monitoring of these subjects will be ongoing throughout the study.

8.7.3 Clinical laboratory evaluations

Summaries of clinical laboratory results will be performed using an 8-number summary by visit and treatment. All subjects in the safety population will be included in these summaries. Baseline is defined as the last value collected prior to first dose of study drug.

The number and percentage of subjects with treatment-emergent laboratory abnormalities within 7 days of last dose of study drug will be summarized by treatment group. In addition, shift from Baseline tables will be generated by visit and treatment group. All summary tables will be repeated for abnormalities that occur during the treatment-free follow-up which is defined as occurring more than 7 days after the date of last dose. The denominator for these will include any subject who entered into the 4 week treatment-free follow-up phase.

All laboratory data will be included in the data listings and all test values outside the normal range will be flagged.

Pregnancy test and FSH will be listed separately.

The laboratory parameters listed in Table 2 on the following page will be assessed for each patient.

Creatinine clearance will be calculated by the central laboratory using the Cockcroft Gault equation and actual body weight:

$$CLCr \text{ (mL/min)} = \{((140 - \text{Age [years]}) \times \text{weight[kg]}) / (72 \times \text{SCr[mg/dL]})\} \times 0.85 \text{ (if female)}.$$

where SCr =serum creatinine

Online calculator can be found at:

https://www.kidney.org/professionals/KDOQI/gfr_calculatorCoc

8.7.4 Vital signs

Vital signs will include systolic blood pressure (mmHg), diastolic blood pressure (mmHg), respiratory rate (breaths/min), heart rate (beats/min), and oral temperature (°C). Vital signs data will be summarized using an 8-number summary by visit and treatment. In addition, the number and percentage of subjects with significant changes in vital signs from Baseline will be summarized by treatment. No statistical testing will be performed. Baseline is defined as the last value collected prior to first dose of study drug.

Criteria for clinically significant changes in vital signs parameters.**Pulse Rate**

- < 50 bpm
- >120 bpm
- 30 bpm increase from Baseline
- 30 bpm decrease from Baseline.

Blood Pressure

- SBP > 150 mmHg or DBP > 100 mmHg
- SBP > 200 mmHg or DBP > 110 mmHg

Respiration Rate

- < 8 breaths/min
- 40 breaths/min

Temperature

- 38.3°C
- 1.1°C increase from Baseline (Baseline > 36.8°C)

Change in Weight

- 5% increase from Baseline
- 5% decrease from Baseline

A by-subject listing will be provided.

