11.7.4. Vital Signs

Vital signs data will be summarized using an 8-number summary by visit and treatment. In addition, the number and percentage of subjects with significant changes in vital signs will be summarized by treatment. No statistical testing will be performed.

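### The vital-sign table of significant changes from Baseline uses level criteria with no Baseline condition, so findings already present before dosing are counted as changes

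*SAP*

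**What the plan says.** Protocol 11.7.4 promises that "the number and percentage of subjects with significant changes in vital signs will be summarized by treatment" and gives no criteria. SAP 8.7.4 adds the reference point: "the number and percentage of subjects with significant changes in vital signs from Baseline will be summarized by treatment". In the same section, "Baseline is defined as the last value collected prior to first dose of study drug".

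The criteria listed there are of two kinds:

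- **Levels, no Baseline term.** Blood pressure "SBP > 150 mmHg or DBP > 100 mmHg" and "SBP > 200 mmHg or DBP > 110 mmHg"; pulse below 50 or above 120 bpm; respiration limits at 8 and 40 breaths/min. Temperature also has one level, at 38.3°C.
- **Changes, referred to Baseline.** Pulse "30 bpm increase from Baseline" and "30 bpm decrease from Baseline"; weight up or down 5%; temperature up 1.1°C, with an added condition on the Baseline temperature.

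The section does not require the Baseline value to be inside a limit, and it does not say which visits count. It states that no testing will be done, and it plans 8-number summaries by visit and a by-subject listing.

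**The concern.** The table's label and its rules do not match. A reader of the study report will take a subject in this table as someone whose vital signs changed after dosing. For the level criteria the rule asks only whether a value lies beyond the limit.

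Nothing in the plan keeps subjects beyond a limit out of the study. The inclusion and exclusion criteria (Protocol 3.1 and 3.2) set no numeric blood pressure or pulse limit, and exclusion 7 leaves cardiovascular conditions to the investigator's judgement.

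Safety and tolerability are a primary objective, and this is the only categorical vital-sign summary in SAP 8.7.4. Laboratory data are treated differently. SAP 8.7.3 counts "treatment-emergent laboratory abnormalities within 7 days of last dose of study drug" and adds shift tables, whereas vital signs have neither. At stake is whether the reported number of subjects with a significant change is a number of changes.

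**Working it through.** The plan states no figure for this table, so there is none to reproduce. The check has three parts.

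**1. Apply the criteria as written to single subjects.**

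| Baseline | On treatment | Change | Counted? |
|---|---|---|---|
| SBP 155 | 151 | −4 mmHg | Yes (>150) |
| SBP 110 | 149 | +39 mmHg | No |
| Pulse 48 | 48 | 0 | Yes (<50) |

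**2. Is a Baseline condition implied elsewhere?** Two places suggest that it is not. The 1.1°C temperature criterion carries an explicit Baseline condition (Baseline above 36.8°C), so the section writes one in where it wants one. In SAP 8.7.6, the significant ECG changes include QTcF values above the sex-specific limits at Screening or Baseline, so in this SAP the phrase does not reliably mean new since Baseline.

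**3. Illustrate the size.** All inputs about blood pressure are assumptions:

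- SBP normal, with mean/SD 130/14, 134/15 or 138/16 mmHg; within-subject correlation 0.6; no drug effect; diastolic pressure ignored.
- Five post-Baseline readings, matching the Day 3 and Week 2, 4, 8 and 12 vital-sign visits in the schedule of assessments.
- Model: reading = mean + subject effect (variance 0.6 × SD²) + visit error (variance 0.4 × SD²).
- Counted: the maximum of the five readings is >150. New: counted and Baseline ≤150. Pre-existing: counted and Baseline >150.

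The share above 150 at Baseline is 1 − Φ((150 − mean)/SD). The other rows come from simulating 1,000,000 subjects per setting.

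| | 130/14 | 134/15 | 138/16 |
|---|---|---|---|
| Above 150 at Baseline | 7.7% | 14.3% | 22.7% |
| Counted by the SAP criterion | 21.5% | 35.1% | 49.1% |
| of which new | 15.9% | 23.5% | 29.5% |
| of which pre-existing | 5.6% | 11.6% | 19.6% |
| Pre-existing share of counted | 5.6/21.5 = 26% | 11.6/35.1 = 33% | 19.6/49.1 = 40% |

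In an arm of 50 the middle setting gives 50 × 0.351 = 17.6 subjects counted, of whom 50 × 0.116 = 5.8 were above the limit before dosing. Adding the end-of-study visit lowers the shares slightly, to about 25%, 32% and 39%.

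**Does the miscount hide a drug effect?** Add an assumed uniform +5 mmHg in an active arm of 50 against 25 on placebo. Divide the difference in proportions by its standard error, √(p₁(1−p₁)/n₁ + p₀(1−p₀)/n₀), first with all subjects and then with new cases over those at risk.

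| | 130/14 | 134/15 | 138/16 |
|---|---|---|---|
| Ratio, SAP criterion | 1.27 | 1.23 | 1.15 |
| Ratio, new cases over at risk | 1.29 | 1.25 | 1.15 |
| SD of chance difference with no drug effect, SAP criterion (points) | 10.1 | 11.7 | 12.2 |
| Same, new cases over at risk (points) | 9.6 | 11.8 | 13.5 |

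The ratios are practically equal. The chance SD is slightly lower under the new-case rule in the first setting, about equal in the second and higher in the third, because the at-risk denominator shrinks.

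**The case against.** Four points can be made for the plan.

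- **A programmer could read changes from Baseline as new occurrences only.** The SAP does not instruct anyone to count pre-existing findings; that follows from the absence of a rule, and the table shells are in a separate document. This stands as a caution. It also means that two programmers could produce different tables from the same text, which the SAP should prevent before unblinding.
- **Other displays show the change.** The by-visit summaries and the listing are planned, the protocol synopsis promises change from baseline for vital signs, and randomization balances pre-existing findings in expectation. This limits the harm but does not correct the count.
- **The laboratory contrast is imperfect.** SAP 8.7.3 uses the term treatment-emergent without defining it for laboratory values. That is fair, so the point does not rest on the contrast.
- **Counting only new cases loses information.** A subject at 152 mmHg who rises to 195 mmHg is in the table now and would drop out. This stands against simply excluding such subjects, and the fix below keeps them visible.

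A reader might also infer that pre-existing hypertension dilutes a drug signal, or that with 25 placebo subjects it materially adds chance imbalance. The documents contain no data to show either, and the calculation above does not support them. Nor is pulse as a whole without reference to Baseline: its two 30 bpm criteria are sound.

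**Conclusion.** The point holds as a counting and labelling defect. The level criteria for blood pressure, pulse and respiration carry no Baseline condition. Read literally, they count a subject who was already beyond a limit and is unchanged or improved. The 38.3°C level has the same form, but oral temperature is scheduled only at Screening, Day 1 and end of study, so it matters little.

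That the criteria lack the condition is a matter of text and needs no assumption. The size is wholly assumed: about 26% to 40% of counted subjects pre-existing over the illustrated range, and the documents cannot narrow it. No primary conclusion depends on the table, which is descriptive and untested. The benefit of a correction is an accurate count of new on-treatment findings, not a material gain in power to detect a drug effect. It is worth making because safety is a primary objective and the change is cheap.

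**What to change.** Add to SAP 8.7.4 a rule such as:

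> For each criterion defined by a level, only post-Baseline values are considered. The table shows (a) subjects who meet the criterion after Baseline and did not meet it at Baseline, with subjects not meeting it at Baseline as denominator, and (b) subjects who already met it at Baseline, in a separate row. Baseline is the last pre-dose value.

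State also which post-Baseline visits count, in particular whether the end-of-study visit is included. The limits themselves need not change, and the 30 bpm, weight and temperature-increase criteria stay as they are.

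The cost is a sentence or two in the SAP, one condition in the program and one extra row per criterion. No new data are needed, since the section already defines Baseline. Subjects who start beyond a limit and worsen remain visible in row (b).
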